Virtual Reality Guided Acupuncture Imagery Treatment for Chronic Low Back Pain

NCT06814470

07/15/2024

The use of imagery to treat illness has a long history in medical practice. Although still under investigation, research findings support the notion that the brain responds in similar ways to imagined experiences as it does to actual experience. Thus, underlying the functional nature of mental imagery may be shared neurocognitive operations that support both imagination and perception. Acupuncture is a unique, invasive treatment modality and has been recommended for the treatment of cLBP by the American College of Physicians. Studies have shown that the experience of acupuncture needle stimulation and the visualization of acupuncture needle stimulation can provoke overlapping activations in brain regions, such as the anterior insula (AI), anterior cingulate cortex (ACC), and periaqueductal grey (PAG).

Based on above findings, *the PI and his team developed a new treatment modality*, whereby participants watch a 2-dimensional (2D) video of acupuncture that was previously administered to their own body and imagine it being concurrently applied, viz., 2D video-guided acupuncture imagery treatment (2D-VGAIT). We found that 2D-VGAIT can produce an analgesic effect in healthy subjects. In a more recent pilot study, we found that 2D-VGAIT can produce comparable symptom relief to real acupuncture after a 1-month (6 treatments) intervention in cLBP patients. Nevertheless, the reality simulation of 2D-VGAIT can be improved.

Recently, Virtual Reality (VR) has drawn the attention of researchers. VR allows for the simulation of physical presence in the real or imagined worlds. As a powerful tool for studying body representation and creating perceptual body-ownership transfer illusions, literature suggests that VR is more effective in reducing pain than 2D screen applications. This unique property of VR may further increase 2D-VGAIT's efficacy.

Specific Aim: Perform a feasibility study of cLBP treatment using the developed VRGAIT system. cLBP patients will be recruited and randomized to VRGAIT and VRGAIT control conditions. Primary outcomes will be feasibility-related assessments (recruitment, retention, fidelity, satisfaction, and safety). Secondary outcomes will be clinical outcomes, presence, imagery vividness, and acupuncture deqi sensations.

Detailed experimental procedure

Subject recruitment. Patients with non-specific cLBP will be recruited.

Randomization. Patients who pass the screening will be randomized to the VRGAIT or VRGAIT control group using a centrally generated, variable-sized block design.

Endpoints. Primary outcomes will be feasibility-related outcomes such as recruitment, retention, fidelity, satisfaction, and safety. Secondary outcomes will include clinical outcomes and vividness and presence scales.

Blinding. Due to the nature of the intervention, patients cannot be blinded as to whether they receive VRGAIT or VRGAIT control. All outcome assessors will be blinded to the treatment each patient receives.

Session 1 will be a baseline session that will include clinical outcome measures and other related assessments and videotaping for VRGAIT treatment. Similar to our previous studies, we will explain the potential underlying mechanism of how imagery treatment works and the procedures for this study. Next, the subject will receive: 1) a brief, real acupuncture treatment,

which will be videotaped using a VR camera; 2) a cotton swab touching non-acupuncture sites, which will also be videotaped as a VRGAIT control condition. All subjects will experience brief acupuncture and swab touch to avoid the potential confounding provoked by brief acupuncture treatment. Subjects will then be introduced to the MGH Acupuncture Sensation Scale (MASS) to report the sensations they experienced during acupuncture treatment and cotton swab touch.

Outcomes

Participant Satisfaction Survey is a 5-point Likert scale (5 = very satisfied; 1 = completely dissatisfied) used to assess participant satisfaction at the end of the study.

29-item Patient-Reported Outcomes Measurement Information System (PROMIS-29): We will use PROMIS-29 to assess pain intensity (using an 11-point numeric rating scale [NRS]), physical function, depression, anxiety, fatigue, sleep disturbance, interference and social role, and activity in the past 7 days.

Pain Bothersomeness Scale: This is a self-reported measure of cLBP pain severity that is commonly used to assess clinical chronic pain. Participants rate how bothersome their LBP was during the previous week with a VAS scale (0–10) from “not at all bothersome” (0) to “extremely bothersome” (10).

MGH Acupuncture Sensation Scale (MASS) is a scale developed to measure sensations evoked by acupuncture treatment. The MASS will be applied after each treatment.

Vividness Scale is a 0-10 vividness scale to measure imagery vividness during the intervention. The scale ranges from Not Vivid/Unclear (0) to Vivid/Clear (10).

Symptoms and Adverse Events: Symptoms and adverse events during or after treatment will be recorded after each treatment.

Sessions 2-7 will be treatment sessions. Subjects will receive VRGAIT or the VRGAIT control based on the randomization across 4 weeks (2 times per week during weeks 1-2, 1 time per week during weeks 3-4).

Session 8 will be an assessment session identical to Session 1.

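### Could patients learn their arm before the self-reported Session 1 baseline, and does the plan need to rule this out?

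*Protocol*

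**What the plan says.** The Randomization paragraph of the Protocol names one condition for entry to an arm: "Patients who pass the screening will be randomized to the VRGAIT or VRGAIT control group". It adds that the sequence is generated centrally in blocks of varying size. It does not give the order of randomisation, release of the arm and Session 1.

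The Blinding paragraph says "patients cannot be blinded as to whether they receive VRGAIT or VRGAIT control", and then "All outcome assessors will be blinded to the treatment each patient receives".

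On the visits, the Protocol says "Session 1 will be a baseline session that will include clinical outcome measures". At that visit staff give an introduction ("we will explain the potential underlying mechanism of how imagery treatment works and the procedures for this study"), and then "All subjects will experience brief acupuncture and swab touch", with both procedures filmed. The arm first comes into use in the paragraph on Sessions 2-7: "Subjects will receive VRGAIT or the VRGAIT control based on the randomization across 4 weeks". The closing visit mirrors the first: "Session 8 will be an assessment session identical to Session 1".

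The SAP labels the analysis of clinical outcomes exploratory. It uses paired pre-post t-tests within each arm and a mixed model with group, time (baseline and 4 weeks) and their interaction. The primary outcomes are recruitment, retention, fidelity, satisfaction and safety.

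**The concern.** Read literally, a patient could be randomised on passing screening, be told the arm, and only then fill in PROMIS-29 and the Pain Bothersomeness Scale. Both are the patient's own ratings, so blinding the assessor does not protect them. Central generation describes how the sequence is made, not when an assignment is released. A patient disappointed or encouraged by the assignment might rate pain differently at baseline.

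That baseline is the pre value for the paired tests and the first time point of the mixed model. A reaction to the assignment would enter both analyses as apparent treatment change. Such contamination would also be avoidable, because nothing done at Session 1 depends on the arm.

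**Working it through.** **Order of events.** Four statements matter, set side by side:

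- Randomization paragraph: passing screening is the condition. No time is given.
- Session 1 paragraph: baseline measures, introduction, needling, swab touch and both recordings, for every subject. No step differs by arm.
- Introduction at Session 1: it covers how imagery treatment may work and what the study involves. It mentions no individual assignment, so it is not evidence of disclosure.
- Sessions 2-7: first use of the assignment.

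No statement puts disclosure before baseline, and none puts it after. The stated reason for giving everyone both procedures is to avoid confounding from the brief needling, so the design already sets out to keep Session 1 alike in both arms.

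**Effect if disclosure did come first.** Let knowledge of the arm add dV to the baseline mean in VRGAIT and dC in control. With both visits observed for everyone,

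interaction = (post - pre in VRGAIT) - (post - pre in control),

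so it moves by -(dV - dC), and the paired changes move by -dV and -dC. For example, (dV, dC) = (0.3, 0) gives -0.3; (0.3, 0.3) gives 0; (0.3, -0.2) gives -0.5. Covariates that are constant over time, such as age and gender, leave this unchanged when the data are complete. If the arm is released after Session 1, this source contributes 0.

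**Which outcomes.** The argument is clear for PROMIS-29 and Pain Bothersomeness only. Vividness is rated during the intervention, and no imagery treatment is given at Session 1, so no baseline value is evident. The timing of the presence measure is not described. At Session 1 the MASS rates real needling and swab touch.

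**How large a shift would matter.** The documents give no sample size, SD or correlation, so the following inputs are assumptions. Coverage of a 95% interval falls to 90% when the bias is k standard errors, where Phi(1.96 - k) - Phi(-1.96 - k) = 0.90, giving k = 0.652. The standard error of the interaction is SD × sqrt(2(1 - rho)) × sqrt(2/n), with n per arm.

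| SD | rho | n per arm | SE | k × SE (points) |
|---|---|---|---|---|
| 2 | 0.5 | 10 | 0.894 | 0.58 |
| 2 | 0.5 | 20 | 0.632 | 0.41 |
| 2 | 0.5 | 30 | 0.516 | 0.34 |
| 1.5 | 0.7 | 30 | 0.300 | 0.20 |
| 2.5 | 0.3 | 10 | 1.323 | 0.86 |

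With a t interval on 18 degrees of freedom, k is 0.69 and the first row becomes 0.62, so the second decimal is not firm. The 90% mark is itself a choice. The table shows how large a shift would have to be; it is not evidence that one occurs.

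**What moving randomisation would do.** Making completion of Session 1 a condition of randomisation would disturb two primary outcomes, because the SAP does not define enrolment, which is the numerator of recruitment and the denominator of retention. Suppose 80 are screened, 40 pass, 8 withdraw at Session 1 and 4 are lost later (all assumed). Completers number 40 - 8 - 4 = 28. Counting all 40 as enrolled gives retention 28/40 = 70.0% and recruitment 40/80 = 50.0%. Counting only the 32 randomised gives 28/32 = 87.5% and 32/80 = 40.0%. That remedy would make two primary outcomes depend on a definition in order to protect exploratory ones.

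**The case for a change.** The best case for acting is that patients' knowledge of the arm at 4 weeks cannot be avoided in this design, whereas knowledge at baseline can. The first is no reason to accept the second. Closing the gap needs no extra visit or procedure: the arm could be withheld until Session 1 ends without moving randomisation, so the denominator problem would not arise. If the team already works that way, one sentence would merely record it.

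Most of this stands. The omission is real, assessor blinding does not cover it, and releasing the arm after baseline is the better order. The order of randomisation and Session 1 could also affect who drops out between them, which touches retention even though no baseline score enters it.

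What does not stand is the step from silence to a defect. The harm requires the team to disclose the arm at a point where the plan has no use for it and nothing tells them to. Following the text does not lead to a wrong result.

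**Conclusion.** No change to the plan is called for. The documents leave the moment of disclosure unstated, and a team running identical Session 1 visits has every reason to release the arm afterwards. In that case the bias from this source is 0.

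If disclosure did come first, the group-by-time estimate for PROMIS-29 and Pain Bothersomeness would be off by -(dV - dC). The documents support no size or sign for that difference. On the assumed inputs it would need to reach roughly 0.20 to 0.86 points on a 0-10 score to bring interval coverage down to 90%, and nothing in the documents suggests that it would. The analyses exposed are labelled exploratory, and their 4-week scores come from unblinded patients in any event. The five primary feasibility outcomes use no baseline score.

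The conclusion rests on reading the Randomization sentence as a statement of eligibility, not timing. A statement elsewhere that patients are told their arm before Session 1 would change it; the Protocol and SAP contain none.

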Virtual Reality Guided Acupuncture Imagery Treatment for Chronic Low Back Pain

NCT06814470

07/15/2024

Biostatistical analysis plan

Consistent with NCCIH recommendations for feasibility studies, we will report the following feasibility outcomes: 1) recruitment: proportion of participant enrolled from the total number of patients screened; 2) retention: proportion of number of subjects who complete all assessments by the total subjects enrolled; 3) fidelity: the proportion of completed/planned intervention sessions (VRGAIT and VRGAIT control); 4) satisfaction: proportion of participants having therapy satisfaction scores above the midpoint; and 5) safety: symptoms and adverse events reported by the participants.

For exploratory analysis of secondary clinical and other related outcomes, we will: 1) perform within-group comparison (pre- vs post-treatment) using paired t-tests to explore the modulation effects of VRGAIT and VRGAIT control on clinical outcomes, deqi sensations, presence and vividness; 2) explore the effects of VRGAIT and VRGAIT control using mixed-model regression. The regression model will include subject as a random effect; fixed effects will include treatment group, treatment time point (baseline, 4 weeks), and their interaction. Covariates such as age, gender, and ERS scores will also be included in the model to reduce subject heterogeneity.

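### The pre/post paired t-test does not fit vividness or deqi as they are measured, and the MASS ratings from the treatment sessions have no stated between-group analysis

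*SAP*

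**What the plan says.** The SAP has one section, the biostatistical analysis plan. Its second paragraph opens "For exploratory analysis of secondary clinical and other related outcomes" and lists two analyses.

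- **Item 1** is a within-group pre/post comparison by "paired t-tests to explore the modulation effects of VRGAIT and VRGAIT control on clinical outcomes, deqi sensations, presence and vividness". It names neither the sessions that supply the two values nor, for deqi, the stimulus being rated.
- **Item 2** is to "explore the effects of VRGAIT and VRGAIT control using mixed-model regression", with a random subject effect and fixed effects for group, "treatment time point (baseline, 4 weeks), and their interaction". It names no outcomes.

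The protocol's Specific Aim lists the outcomes concerned: "Secondary outcomes will be clinical outcomes, presence, imagery vividness, and acupuncture deqi sensations". The Endpoints paragraph says "Secondary outcomes will include clinical outcomes and vividness and presence scales". Neither gives timing.

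On measurement, the protocol says this:

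- **Session 1:** "Session 1 will be a baseline session that will include clinical outcome measures and other related assessments and videotaping for VRGAIT treatment". Every patient has brief real needling and a real swab touch and is introduced to the MASS to report the sensations from both.
- **Outcomes:** the MASS follows every treatment. The vividness scale rates imagery while the intervention is under way.
- **Sessions 2-7** are the treatments. **Session 8** is an assessment described as the same as Session 1.

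**The concern.** A paired pre/post test needs the same quantity measured before and after treatment. That holds for PROMIS-29 and pain bothersomeness. Vividness of guided imagery, and the sensations the VR session evokes, are properties of the treatment session itself and have no obvious counterpart before treatment starts.

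Two things are at stake. First, the analyst must choose the pair, possibly after seeing the data, and the candidate pairs answer different questions. Second, the informative comparison may be missed. The MASS data collected after each treatment can show whether VRGAIT evokes more deqi than its control, but the SAP states no between-group analysis of them.

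**Working it through.** The plan has no figure to reproduce: neither document gives a sample size, significance level, expected effect or correlation for these outcomes. The check sets each outcome in item 1 against the protocol's schedule. There are 2 × 2 + 2 × 1 = 6 treatments (two a week in weeks 1-2, one a week in weeks 3-4).

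| Outcome | Before treatment | Sessions 2-7 | Session 8 |
|---|---|---|---|
| PROMIS-29, bothersomeness | Session 1 clinical measures | not stated | yes, as a repeat of Session 1 |
| Vividness | none described | where its definition places it | none described |
| MASS | real needling and real swab | after each of 6 treatments | real stimuli again, if the repeat is literal |
| Presence | not stated | not stated | not stated |

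**Vividness.** There are 0 described pre-treatment ratings and 6 sessions at which the definition allows one. The pair is undefined.

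**MASS.** At least three pairs are possible:

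1. Session 1 vs Session 8: real vs real. This is coherent, but it measures response to real stimulation.
2. Session 1 vs a treatment session: real vs VR-guided. Any change includes the change of stimulus.
3. First vs last treatment (Session 2 vs Session 7): VR-guided vs VR-guided. This measures change during treatment.

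The SAP selects none. It also does not say whether the Session 1 value is the needling report, the swab report or both.

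**Item 2.** If it covers these outcomes, it supplies a between-group contrast, but only at baseline and 4 weeks. That leaves the MASS ratings across Sessions 2-7 without a stated comparison, and vividness without a described baseline.

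**Illustration for pair 2 only.** The gap, the correlation r and n are all assumed. Take unit SD, two-sided 0.05, no arm difference in treatment ratings and no change over treatment.

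- *Item 1.* Standardised change = gap/√(2(1−r)). With gap 0.5 SD and r = 0.5 this is 0.5/√1 = 0.5. At 20 per arm the noncentrality is 0.5 × √20 = 2.24 on 19 df, which gives p < 0.05 with probability 0.56 (0.29 at 10 per arm, 0.75 at 30). At 20 per arm it runs from 0.19 (gap 0.25) to 0.92 (gap 0.8), and at gap 0.5 from 0.43 (r = 0.3) to 0.78 (r = 0.7). This is power to detect the assumed change of stimulus, not a treatment effect.
- *Item 2.* If the real-to-VR gap is equal in both arms, it cancels and the group-by-time test keeps its 0.05. Suppose instead that each arm's baseline is its own stimulus and real needling is rated 0.5 SD above real swab. The noncentrality is then 0.5 × √(20/2) = 1.58 on 38 df, which gives 0.34 (0.19 at 10 per arm, 0.48 at 30). At 20 per arm it runs from 0.12 (0.25 SD) to 0.69 (0.8 SD).
- *Precision at 20 per arm.* The 95% CI half-width is 2.024 × √(2V/20). For the difference in change, V = 2(1−r); for the mean of six treatment ratings, V = (1+5r)/6. At r = 0.3, 0.5 and 0.7 the half-widths are 0.76, 0.64 and 0.50 SD for change, and 0.41, 0.49 and 0.55 SD for the mean. The mean is therefore not always more precise. The two also estimate different things, so the case for it rests on relevance, not width.

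**The case against.** The strongest reply is that item 1 speaks of pre- and post-treatment, Session 1 is the baseline and Session 8 is its repeat after treatment ends, so the intended pair is Session 1 vs Session 8. For MASS that is a fair reading and the more natural one, and on it no real-to-VR mixing occurs. It is not certain. The protocol's line on Session 8 is terse; taken literally it would also repeat the videotaping that prepares for treatment. On this reading the pair still does not measure sensations during VRGAIT, so the mismatch stands in another form.

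For vividness, a reader might infer that the test is impossible. The documents do not support that. Session 1 includes further assessments that are not itemised, and a first-versus-last-treatment pair could be formed. But nothing places a vividness rating at Session 1, and the scale's definition points away from it.

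It is also fair that one sentence naming the sessions would make item 1 executable. It would not supply the missing comparison of MASS during treatment. The within-group question can stay as an exploratory one; the addition answers a different and more direct question.

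**Conclusion.** The point holds in limited form and should be corrected before analysis. Item 1 states a test that does not fit how vividness and deqi are measured. The vividness pair is undefined. On either Session 1-based reading, the MASS pair does not measure sensations during VRGAIT, and the treatment-session MASS ratings have no stated between-group analysis. This rests on the schedule alone and needs no assumed numbers.

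Three stronger inferences are not supported. The documents do not show that the MASS result will be biased: that requires a treatment session as the post value, and for item 2 also arm-specific baselines. The probabilities above illustrate assumed values and are not evidence of bias in this trial. Nor do the documents show an error for presence, whose timing is simply not given. And the plan is not without any between-group analysis, since item 2 may cover these outcomes at baseline and 4 weeks.

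The scope is exploratory secondary outcomes. Recruitment, retention, fidelity, satisfaction and safety are untouched, as are PROMIS-29 and bothersomeness.

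**What to change.** 1. **MASS.** Add to the exploratory analysis a between-group comparison of the Sessions 2-7 ratings: a mixed model with group, session and random subject, or each patient's mean if the sample is small. Report the difference with a 95% CI. Use Session 1 MASS at most as a covariate, with the same rating or ratings in both arms. Any within-group change during treatment should compare the first with the last treatment session.
2. **Vividness.** Replace the pre/post t-test with a between-group comparison of ratings made during treatment, and state the sessions at which it is rated.
3. **Session 8.** State whether the real stimuli and the MASS are repeated. If so, report Session 1 vs Session 8 separately, by stimulus where rated separately, as response to real stimulation.
4. **Clinical outcomes.** Keep baseline vs 4 weeks for PROMIS-29 and bothersomeness, and say which outcomes item 2 covers.
5. **Presence.** State when it is recorded.

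**Cost.** MASS needs SAP wording only, because the ratings are already planned after every treatment. Vividness and presence need a timing sentence each. Vividness must be recorded at treatment sessions, as its definition implies; if that is not current practice, ratings are added. There is a little more exploratory analysis to report.

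### The exploratory mixed model does not adjust for the baseline score, so its between-arm estimate is valid but usually less precise than it could be

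*SAP*

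**What the plan says.** The second paragraph of the SAP opens "For exploratory analysis of secondary clinical and other related outcomes" and lists two analyses. The first is a paired t-test within each arm, which gives no comparison between arms. The second is a mixed-model regression: "The regression model will include subject as a random effect", and the "fixed effects will include treatment group, treatment time point (baseline, 4 weeks), and their interaction". On adjustment it says: "Covariates such as age, gender, and ERS scores will also be included in the model to reduce subject heterogeneity".

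The SAP does not name the baseline value of the outcome as a covariate and does not set the two arms' baseline means equal. It does not say which coefficient is the treatment contrast; for change from baseline, that is the group-by-time interaction.

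The baseline scores will be available. The Protocol states that "Session 1 will be a baseline session that will include clinical outcome measures and other related assessments", and that "Session 8 will be an assessment session identical to Session 1". The pain bothersomeness item has a recall period ("Participants rate how bothersome their LBP was during the previous week"), and PROMIS-29 refers to the past 7 days, so both can be scored before and after treatment.

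**The concern.** With baseline as a response and a free group effect, the model estimates a separate baseline mean for each arm, although randomisation makes any baseline difference a chance one. The interaction subtracts that chance difference in full. Baseline and follow-up are imperfectly correlated, so full subtraction over-corrects. With equal SDs, (1 − rho) times the chance imbalance remains in the estimate with its sign reversed, where rho is the correlation between the two scores.

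The SAP gives its covariates the job of absorbing differences between patients. For this contrast, with complete data, they cannot do so. A reader of the SAP would expect a gain in precision that does not occur.

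This model supplies the plan's only between-arm clinical estimate, so the width of its confidence interval is what is at stake. The point is confined to PROMIS-29 scores and pain bothersomeness.

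**Working it through.** **Inputs.** The model terms come from the SAP. The documents state no sample size, allocation ratio, SD, correlation or alpha, so there is no planned figure to reproduce. Assumed: 1:1 allocation, n per arm, N = 2n, equal SDs at both times (results in SD units), and rho from 0.3 to 0.8.

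**Step 1: what the interaction estimates.** Let D0 and D1 be the differences in arm means at baseline and 4 weeks. The interaction is D1 − D0. Given D0, the expected value of D1 is the treatment effect plus rho × D0. The interaction's expected value is therefore the effect minus (1 − rho) × D0. The adjusted estimate is D1 − b × D0, with b estimating rho. D0 averages zero under randomisation, so both are unbiased.

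The identity was checked by REML fits of the SAP model, with age, gender and ERS included, to three simulated complete data sets (12 per arm, rho 0.3, 0.5 and 0.7). The interaction was −0.7217, −0.5990 and −0.1318. The raw difference in mean change was the same each time, and the standard errors agreed to about five decimals.

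**Step 2: variances.** With k covariates in the ANCOVA, counting baseline, and the others unrelated to outcome:

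- Interaction (change score): 2(1 − rho)(2/n)
- Baseline-adjusted: (1 − rho²)(2/n)(N − 3)/(N − 3 − k)
- Ratio: [(1 + rho)/2] × (N − 3)/(N − 3 − k), which tends to (1 + rho)/2 in large samples

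At 20 per arm with k = 1 the small-sample factor is 37/36. At 10 per arm it is 17/16. With k = 4 (baseline plus the three SAP covariates) the factors are 37/33 and 17/13.

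| Variance ratio, complete data | rho 0.3 | rho 0.5 | rho 0.7 | rho 0.8 |
|---|---|---|---|---|
| 20 per arm, baseline only | 0.668 | 0.771 | 0.874 | 0.925 |
| 10 per arm, baseline only | 0.691 | 0.797 | 0.903 | 0.956 |
| 20 per arm, ANCOVA with three more covariates | 0.73 | 0.84 | 0.95 | 1.01 |
| 10 per arm, ANCOVA with three more covariates | 0.85 | 0.98 | 1.11 | 1.18 |

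**Step 3: interval width at rho = 0.5, baseline only.**

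- 20 per arm: variances 2 × 0.5 × 0.1 = 0.100 and 0.75 × 0.1 × 37/36 = 0.0771. With t on 38 and 37 df, the half-widths are 0.640 and 0.563 SD.
- 10 per arm: variances 0.200 and 0.75 × 0.2 × 17/16 = 0.1594. With t on 18 and 17 df, the half-widths are 0.940 and 0.842 SD.

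**Step 4: where the gain ends.** Setting the ratio to 1 gives rho = 1 − 2k/(N − 3). For baseline alone this is 1 − 2/37 = 0.95 at N = 40 and 1 − 2/17 = 0.88 at N = 20. For ANCOVA with k = 4 it is 1 − 8/37 = 0.78 and 1 − 8/17 = 0.53.

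**Step 5: dropout.** Simulation (8,000 runs per cell) compared the SAP interaction without covariates, all patients kept, with completers' ANCOVA on baseline alone. With 20% of 4-week scores missing completely at random, the ratios at rho 0.3, 0.5, 0.7 and 0.8 were 0.699, 0.808, 0.908 and 0.949 at 20 per arm, and 0.751, 0.856, 0.948 and 1.002 at 10 per arm.

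**Step 6: the common-baseline model.** Without further covariates, its group difference equalled the completers' ANCOVA estimate to four decimals in four simulated data sets, with and without missing 4-week scores. The baseline-only ratios therefore describe either remedy. With the three SAP covariates kept as main effects and complete data, the common-baseline model loses less than ANCOVA. Simulated ratios were about 0.84 at rho 0.5 and about 1.0 at rho 0.8 for 10 per arm, and about 0.7 to 0.93 over rho 0.3 to 0.8 for 20 per arm.

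**The case against.** The strongest reply is that little turns on this. The planned estimate is valid, the analysis is exploratory, the primary outcomes are feasibility measures, and no test or progression rule uses the contrast. At 10 per arm the interval stays wide either way. All of that stands and limits the weight of the point. It does not argue for the wider interval.

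Second, the covariate list is open-ended, so baseline could be added to it. That would not help. Adding the baseline score as a main effect to the SAP model left the interaction unchanged in three further fits at 20 per arm (−0.4925, 0.7306 and −0.3432 before and after), and the random-intercept variance fell to about zero. The form of the model has to change.

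Third, the baseline-only ratios assume that the SAP's other covariates are dropped. If they are kept in an ANCOVA at 10 per arm and are unrelated to outcome, the gain is nearly gone at rho 0.5 (0.98) and becomes a loss at 0.7 (1.11). This is a fair limit on the ANCOVA option and a reason to prefer the common-baseline model. Covariates that predict outcome would do better, but the documents do not show whether these do.

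Fourth, every size rests on assumed values. At 5 per arm, baseline adjustment alone gave simulated ratios of 0.98 at rho 0.7 and 1.11 at rho 0.9, so the gain is usual, not certain.

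**Conclusion.** The concern holds. The interaction is the unadjusted difference in mean change when data are complete, and the named covariates do not sharpen it. This is a matter of efficiency, not bias, in an exploratory analysis.

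The algebra is secure; the size of the benefit is conditional on the assumed sample size, correlation, 1:1 allocation and equal SDs. At 10 to 20 per arm with complete data, adjusting for baseline alone lowers the variance by roughly 4% to 33% for correlations from 0.8 down to 0.3. The gain shrinks with dropout, which is an open question here because retention ("proportion of number of subjects who complete all assessments by the total subjects enrolled") is itself an outcome under study. It can disappear with very small arms, very high correlation, or an ANCOVA carrying several uninformative covariates. Within those limits, it is a worthwhile improvement from data the trial already collects.

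**What to change.** For PROMIS-29 scores and pain bothersomeness, replace the mixed-model specification with one of these:

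- **Preferred:** a longitudinal model of the baseline and 4-week scores with a common baseline mean (no group effect at baseline), a group effect at 4 weeks, and unstructured covariance.
- **Alternative:** ANCOVA of the 4-week score on group and the same measure's baseline score.

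Name the adjusted 4-week group difference as the treatment contrast, report it with its 95% CI, and label it exploratory. Keep few or no other covariates if the arms are small.

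The cost is a change of SAP wording, including a shorter covariate list, and about one residual degree of freedom (38 to 37 at 20 per arm). If ANCOVA retained all three SAP covariates as well, it would be four (38 to 34). No new data are needed. ANCOVA drops patients without a 4-week score. The common-baseline model keeps them in the analysis, although in the checks without further covariates they did not move the estimated group difference.
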